double dose (24 mg) of BUP. Participants with truncated study visits due to COVID-19 will receive a lockbox for medications taken on days when they do not attend clinic (Tuesday, Thursday, and weekends) during the detox phase. Staff will ensure that participants sign medication accountability logs. Participants receive 12 mg of BUP on days 1 and 2 of week 2. Beginning on day 3 (Wed) of week 2, all participants will begin a 10-day BUP detox schedule [129], such that they receive 8 mg for two days, 6 mg for 1 day, 12 mg dose on Sat (double dose to cover Sun, or 6 mg doses on Saturday and Sunday if they are receiving take-home medications due to COVID-19), 4 mg on day 1 of week 3, 2 mg on days 2 and 3, and 1 mg on days 4 and 5 (Thur-Fri) of week 3. Participants may receive take-home dose(s) of buprenorphine to ensure participants are receiving the medication according to the dosing regimen on holidays and holiday weekends when the clinic is closed. This may also occur when inclement weather is forecast and the decision is made to have the clinic close on a given day. If a participant initially experiences side effects (e.g., feeling high) on the 8 mg dose of buprenorphine (which does occur during the first day or two of buprenorphine induction in a subset of opioid dependent patients), the physician may delay the increase to 12 mg depending on symptoms severity and duration; however, the participants will typically be on a stable dose of buprenorphine before day 3 of week 2. If a participant cannot tolerate the 12 mg dose of buprenorphine their dose will be reduced to no less than 8 mg/day and the detox schedule will be adjusted accordingly. If the participant cannot tolerate 8 mg of buprenorphine they will be discharged from the study. In the event that a participant is quarantined due to COVID-19 during phase I BUP detox, they will be discharged from the protocol and the study physician will provide them with take-home BUP taper individually tailored according to where in phase 1 the participant was at the time of quarantine.

During the detox phase, morning GBP/placebo ingestion will occur under supervision 6 days per week, and a take-home dose will be given each day for evening ingestion (3 take-home doses on Sat to also cover Sun). For participants on the truncated schedule due to COVID-19 (thrice weekly), lockboxes with BUP and GBP/Placebo will be given on the same schedule to be taken on days when not presenting to clinic (Tues, Thurs, weekends) with specific instructions provided by CAST nurse, in addition to drug accountability logs signed by the participant. Additional take-home doses of GBP/placebo will be given to take on holidays, days when clinic is closed due to inclement weather and holidays to ensure adequate blood levels of GBP are maintained. The initial dose of GBP at 100 mg will be given on day 3 of week 1, and a 100 mg dose provided to take home. The GBP dose will increase to 200 mg BID on day 4, 400 mg BID on day 5, 600 mg BID on day 6, and 800 mg BID (1,600 mg/day) on day 7 of week 1. Participants will remain on 1600 mg/day through day 2 of week 5 (during NTX therapy, GBP/placebo capsules will be given in weekly blister packs). Then GBP will be reduced to 1200 mg/day on day 3, 800 mg/day on day 4, 600 mg on day 5, 400 mg on day 6, and 200 mg on day 7. On days 1 and 2 of week 6, all participants will receive placebo. If GBP side effects are too severe at the 800-mg BID dose, GBP will be decreased to no less than 1200 mg/day, given data that 900 mg/day of GBP is ineffective [97]. If GBP side effects are too severe at 1200 mg/day, GBP will be discontinued and the participant will be discharged from the study and referred to local treatment agencies. During transition to NTX (week 4), if a) the participant's urine sample is opioid-negative and/or regular opioid use is not indicated, *and* b) orthostatic vital signs and symptoms are within limits specified below (Section 14, Protection of Participants, B. Protections Against Risk): On day 1 of week 4, participants will receive 0.1 mg of clonidine followed 20-30 min later by 6.25 mg of oral NTX. If tolerated, the person will return on day 2, receive 0.1 mg of clonidine followed 20-30 min later by 6.25 mg of oral NTX. On day 3, participants will receive 12.5 mg of NTX 20-30 min after clonidine. (For those who do not start induction until day 2 or 3: Starting on day 2, NTX will be given at the 6.25 mg dose 20-30 min after clonidine. On day 3, NTX will be given at the 12.5 mg dose 20-30 min after clonidine.) On day 4, 25 mg of NTX will be given 20-30 min after clonidine. If 25 mg is tolerated, then on the morning of day 5, participants will receive the depot NTX injection. (Participants have up to day 3 of week 4 to start the transition to NTX. For those who do not start induction until day 2 or 3: Starting on day 2, NTX will be given at the 6.25 mg dose 20-30 min after clonidine. Starting on day 3, NTX will be given at the 12.5 mg dose 20-30 min after clonidine. In such cases, dosing/administration on subsequent days will be as specified above.) Those

who received the first NTX injection, and who have been determined to be eligible for the second NTX injection and choose to receive a second NTX injection, will do so during their week 8 clinic visit. If a participant is required to quarantine due to COVID-19 during phase II, they may remain on protocol and complete assessments and therapy sessions remotely (by phone or teleconference). If this occurs, urine drug screens and the COWS assessment will be recorded as missed until they are no longer required to quarantine. If a participant is unable to provide a urine drug screen at week 8 due to quarantine, they will not be eligible for the second Vivitrol injection and will be discharged from protocol and offered referrals to treatment as necessary.

- D. Medication Compliance. During the detox phase/week 4 oral NTX phase, compliance with BUP, oral NTX, and GBP/placebo (AM dose) will be assured by observing participants as they ingest the medication and/or providing lockboxes and accountability logs signed by participants that are in the protocol on the truncated schedule due to COVID-19. Compliance with take-home doses of GBP during the detox and weekly blister packs of GBP during/immediately following week 4 depot NTX will be monitored by pill counts, self-report, and/or week-4 blood levels of GBP. Riboflavin will be added to capsules and weekly urine samples will be stored for back-up quantitative urinalysis of riboflavin levels, especially if GBP blood levels are disparate. The research nurse will perform depot NTX injections.
- E. Randomization of sample. To increase the likelihood that treatment groups are balanced with respect to key baseline variables (opioid-withdrawal symptom severity, marijuana-use status, anxiety ratings and tobacco-use status), males and females (with and without prescribed psychoactive medication) will be separately assigned to treatment groups with “urn” randomization, using a Microsoft Access program developed and used in previous studies [130, 131]. In urn randomization, an algorithm modifies ongoing randomization probabilities based on prior composition of treatment groups, maximizing multivariate equivalence of treatment groups [132]. Thus, urn randomization balances allocation of important prognostic variables in treatment groups, while retaining other benefits of random assignment [133, 134].
- F. Maintenance of the Double Blind - A code will be kept in a locked cabinet, in a special file in the data manager’s or PI’s office, and pharmacy matching participants with the active/placebo study medications. This code will be available 24 hours a day and will be broken at the request of outside health professionals in the event of a medical emergency. To prevent any of the investigators from inadvertently discovering the medication assignments of other participants in the special file needs to be opened, a psychiatrist not directly involved with the study participants will open the special file. Once the code is broken, that participant will be dropped from the study. Although we do not anticipate difficulties maintaining the double blind, we will evaluate the adequacy of the double blind by having each participant and a research staff member report the medication (placebo or gabapentin) they believe is being administered.
- G. Counseling Guidelines - Several components of Behavioral NTX therapy [135] will be employed in the present study. During the BUP/GBP induction and detox phase, all participants will be scheduled to meet weekly, either in person, via telephone or video conference, with a research therapist typically for 60 minutes. Content of these sessions will include education and support, medication management, techniques to enhance motivation for abstinence or NTX therapy, and review of contingency management procedures. The session also provides an opportunity to review critical issues and problem areas. During NTX treatment, weekly sessions with the research therapist will include Cognitive Behavioral Treatment, manual-driven [136, 137] as a controlled element of the study. Modules will focus on relapse prevention and engagement in community support groups (e.g., Narcotics Anonymous). Although the involvement of a significant other in the treatment process will be encouraged, it will not be required for participation. The research therapist will monitor number and duration of scheduled treatment sessions, including frequency and reason for extra-session telephone calls, subjects’ involvement in any ancillary treatments, and other clinically significant events and formal treatment concurrent with their study treatment (including self-help meetings). At the end of the study, participants will be given treatment referrals.

- H. **Program Termination** - Any participant choosing not to take the study medication will be discharged from the study with appropriate referrals. During the detox phase and NTX transition week, participants missing medications on three successive days (or any two days during week 1) or do not complete assessments will be administratively discharged. If participating under the truncated schedule due to COVID-19, participants will be discharged if they miss any clinic visits during week 1 and miss 1 clinic day during weeks 2 and 3 due to the take-home medication schedule, therefore, they cannot miss Friday visits. Participants will be discharged if they do not receive their take-home medication blister packs by day 5 of week 4. Participants who cannot provide an opioid-free urine on either day 1, 2, or 3 of week 4 during oral NTX induction may be deemed ineligible to continue onto depot NTX therapy as determined by the study physician. Similarly, if participants are unable to provide an opioid-free urine at the week 8 visit, a study physician will determine if participants will be eligible to continue in the study with or without the second NTX injection. A participant will be discharged if PIs believe a subject's health or wellbeing may be threatened by continuation in the study. If a participant is required to quarantine due to COVID-19 during the phase I BUP detox, they will be discharged from the protocol, and the study physician will provide take-home BUP taper for detox. If a participant is required to quarantine due to COVID-19 during phase II, they may remain on protocol and complete assessments and therapy sessions remotely (by phone or teleconference). If this occurs, they will be unable to provide urine drug screens or complete the COWS assessment until they are no longer required to quarantine. If a participant is unable to provide a urine drug screen at week 8 due to quarantine, they will not be eligible for the second Vivitrol injection and will be discharged from protocol and offered referrals to treatment as necessary. If a pregnancy test becomes positive, the participant will be withdrawn from the study and referred to an appropriate treatment program. Participants who relapse following BUP detox or NTX therapy, as determined by physician assessment, will be offered referrals to the UAMS Center for Addiction Services and Treatment, a residential therapeutic community, an inpatient treatment program, or others, as appropriate. Participants administratively discharged will also be referred to local treatment programs, if desired.
- I. **Dependent Measures**. The purpose and timing of assessments are shown in **Table 1**. Assessments will be presented via computer whenever possible with responses entered directly into the computer (with paper copies as backup in case of computer malfunction or unavailability). If an assessment is missed at any time point, whether due to participants missing appointments, glitches with computer or staff error, the assessments will be completed at the next earliest visit as possible and appropriate. If not, the assessment will be considered missed.
- The primary outcome measure is illicit opioid use (typically obtained thrice weekly during weeks 1-4, weekly during weeks 5-12, and once at the week 16 follow-up interview, biologically verified by the Redwood Toxicology Laboratory and/or Lochness Medical Supplies dipstick and/or EMIT assay). Secondary outcomes include craving ratings, retention, self- and observer-rated opioid withdrawal symptoms, adverse events, sleep quality, withdrawal signs (blood pressure, body temperature), mood, heart rate variability (HRV), decision making, and prescription opioid and other drug use, including alcohol, tobacco and caffeine. We chose assessment techniques as recommended in NIDA's A Diagnostic Source-book for Drug Abuse Treatment and Research to use comparable assessments by different investigators in substance abuse [138]. Our set of screening instruments will provide general patient information, including demographic data; medical history; and history of substance use, family substance abuse, and psychiatric treatment [130, 131]. Other assessments include the following: **1) Weekly Drug Use** (done weekly), which uses a timeline recall method that we developed in previous studies to assess self-reported use of opioids and other drugs [130, 131]; **2) PRISM 5** (done at intake or during week 1), a computerized structured clinical interview (software package will be purchase) from completed to determine several DSM-V psychiatric diagnoses [139, 140]; **3) Medication Side Effects Checklist** (done weekly), consisting of multiple items describing side effects specific to GBP, BUP or NTX [141] rated on a scale from 0 (not at all) to 4 (very much); **4) Subjective Opiate Withdrawal Scale (SOWS)** (done thrice weekly during weeks 1-3, daily (5 days) during week 4, and weekly thereafter), consisting of 16 items describing possible opioid withdrawal symptoms that are rated on a scale from 0

(not at all) to 4 (extremely) [142]; **5**) *Clinical Opiate Withdrawal Scale* (COWS) (done thrice weekly during weeks 1-3, daily (5 days) during week 4, and weekly thereafter), an observer-rated opioid withdrawal scale that consists of 11 items describing withdrawal symptoms [142]; **6**) the *Stages of Change Readiness and Treatment Eagerness Scale* (SOCRATES) [122]; **7**) measures of distress tolerance, including *Breath Holding Endurance* [143], in which the length of time (seconds) that participants can hold their breath is measured, and the *Distress Tolerance Scale* [144]; **8**) measures of anxiety/depression, including the *State Trait Anxiety Inventory* (purchased through Mind Garden, Inc) [145], the *Anxiety Sensitivity Index* (purchased at anxietysensitivityindex.com from IDS Corporation, Inc.), a reliable and valid 16-item self-report questionnaire that assesses the degree to which an individual is concerned about the possible negative consequences of arousal-based anxiety symptoms [146], and the *Hamilton Anxiety and Depression Scales* [147, 148]; **9**) measures of sleep quality, including the *Pittsburgh Insomnia Rating Scale* [149] and *Pittsburgh Sleep Quality Index* [150]; **10**) measures of known physiological indicators of withdrawal (vital signs, body temperature); and **11**) the *Endpoint Rating Form*, which assesses functional level at termination and reason for termination. To assess potential adverse effects of the study medication, participants will be asked at every visit whether they are experiencing any symptoms, which will be recorded on a Symptoms Form.

Decision Making Assessment. Delay discounting will be assessed via paper survey at intake and at the end of detoxification (week 3, day 5) [151, 152]. Participants will complete 27 fixed-choice options between immediate, smaller and delayed, larger hypothetical amounts of money (e.g., “Would you prefer (a) \$54 today or (b) \$80 in 30 days?”). Delayed amounts of money range from small (\$25-\$35), medium (\$50-\$60), to large (\$75-\$85). Rates of delay discounting will be characterized by calculating k values based on Mazur’s hyperbolic discounting function [153] for choices in each of the three delayed monetary categories. For this study, k values will be averaged across the three monetary categories and log transformed. Higher average k values indicate increased delay discounting.

Heart Rate Variability (HRV). On day 2 or 3 of weeks 1-2 and day 5 of week 3, participants undergo a 10 min assessment of Heart Rate Variability (as a noninvasive measure of relative autonomic nervous system imbalance such as stress versus relaxation) while sitting, standing and sitting while performing measured breathing prior to receiving that day’s medication. Participants will be asked to secure a belt with sensors around their torso as well as place another sensor on their finger and to refrain from talking during the assessment. After approximately 30 seconds after settling down, participants will be given instructions to sit quietly and their HRV will be recorded for 2 minutes. Then the participant is instructed to stand quietly and their HRV will be recorded for 2 minutes. Finally, the participant will be instructed to sit quietly and follow a measured breathing indicator (i.e., inhaling and exhaling) on the computer screen while their HRV is recorded for 2 minutes. HRV will be measured using the HRV System - ProComp2 with Biograph 2,069.10 2,069.10 Infiniti & HRV Suite Software with 1 BVP Sensor/1 Respiration Sensor.

Objective Distress Tolerance Tasks. On day 3 of week 1 prior to receiving active/placebo study medication, participants will be invited to complete two computerized games. The purpose of this preliminary testing is to test the relevance of a quantitative measure of affective distress tolerance (mirror tracing task) and effortful performance (EffRT) with Opioid Use Disorder severity, to self-report measures of distress tolerance, and treatment outcomes.

1) Mirror Tracing Task. This task measures distress tolerance as persistence on the task. In this task, participants use a computer mouse to move a cursor around a monitor to trace over a star shape without leaving the shape’s lines. The mouse is programmed to move the red dot in the reverse direction. If the participant moves the red dot outside of the lines of the star, or stalls for more than 2 sec, the red dot returns to the starting position and there is a loud buzzing noise. There is a simple

practice task before the experimental task. In the experimental task, participants can end the task at any time, but the longer they persist in the task the more points they earn. This task lasts up to 20 min.

2) Effort Expenditure for Reward Task (EffRT). This task measures effort-based decision making. On each trial, participants choose between two different task difficulty levels to obtain monetary rewards. For all trials, participants make repeated manual button presses within a short amount of time. Each button press raises the level of a “bar” viewed onscreen. If the bar is raised to the top within the allotted time period, the participants wins the points for that trial. Each trial offers a choice between two levels of difficulty: a “hard” task and an “easy” task. Hard task trials required the subject to make 100 button presses using the non-dominant little finger within 21 seconds, while easy task trials require the subject to make 30 button presses using the dominant index finger within 7 seconds. Completion of easy task trials will earn 1 point. Hard task trials could earn between 1.24 and 4.30 points. However, the probability of earning the points for successful task completion is 88%, 50%, or 12%. The probability of earning points is indicated onscreen at the start of each trial. At the end of each trial, participants are shown whether they completed the task on time or not, and earned the points or not. Participants have 20 min to play as many trials as they are able.

For completing these optional tasks, participants will be compensated \$20 plus they can earn up to an additional \$5 per task (\$30 total) based on their performance.

Table 1. Summary of the Schedule and Purpose of Assessments.									
PURPOSE/INSTRUMENT	Rater	TIME OF ADMINISTRATION							
		Phase I BUP/GBP				Phase II GBP/NTX			
		Pre-TX	3 X Weekly	Weekly (typically Day 3)	Day 5 Week 3	Days 1 and/or 2 NTX transition	Days 4 and/or 5 NTX transition	Weekly (typically Day 3)	Week 16 (+/- 1 week)
Screening Variables and Predictors of Outcomes									
Demographics Form	RS	X							
Medical History	RS	X							
Substance Use History	RS	X							
PRISM-5	RS	X [^]							
Distress Tolerance Scale	P	X [^]			X			X**	X
Breath-holding Endurance	RS	X [^]			X			X**	X
Mirror tracing task	RS	X [^]							
EffRT task	RS	X [^]							
State Trait Anxiety Inventory	P	X [^]			X			X**	X
Anxiety Sensitivity Index	P	X			X			X**	X
SOCRATES	P	X [^]			X				
Columbia Suicide Severity Rating Scale	P	X+							
Assessment of Outcome: Substance Use									
Urine Drug Screens (12 panel)	P	X	X			X	X	X	X
Weekly Drug Use	RS	X		X				X	X
Weekly Craving	RS			X				X	X
Physical/Psychological Symptoms									

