- 6) have a seizure disorder
- 7) physiological dependence on alcohol or drugs other than opioids, tobacco or marijuana (as determined by physician assessment)
- 8) are pregnant, plan to become pregnant, have inadequate birth control, if relevant, or lactating
- 9) report ongoing use of OTC or prescription drug (including Maalox) that would have major interaction with study drugs, including CNS depressants (e.g., anxiolytics, antidepressants, antihistamines).
- 10) have any of the following: liver function tests >3 times normal, BUN and Creatinine outside normal range; ECG abnormalities including but not limited to: bradycardia (<50 bpm); prolonged QTc interval (>450 msec); Wolff-Parkinson White syndrome; wide complex tachycardia; 2nd degree, Mobitz type II heart block; 3rd degree heart block; left or right bundle branch block; pre-existing severe gastrointestinal narrowing (pathologic or iatrogenic).

Individuals with anxiety or depression and not taking exclusionary medications will be included unless findings during screening indicate a need for immediate treatment determined by the study physician and/or the Columbia–Suicide Severity Rating Scale [128].

C. Initial Diagnostic Evaluation

- 1) Medical—Care will be taken to exclude medically ill participants from the clinical trial by having participants undergo a comprehensive evaluation, including physical, psychiatric, and neurological examinations. Routine laboratory studies will ensure that participants are medically acceptable for participation (CBC, BUN/creatinine, electrolytes, liver-function tests, pregnancy test for women, urinalysis, ECG). Liver function tests will be repeated at week 4. A physician will review laboratory data and ECG prior to study entry. Women of childbearing potential will have a pregnancy test before starting the study and prior to oral NTX. If a woman suspects she has conceived during the study a pregnancy test will be done at her request.
- 2) Psychiatric/Behavioral—Care will be taken to assure that participants meet diagnostic criteria by means of a screening interview by one of the physician investigators.

7. Experimental Methods:

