If participants receive naltrexone 6.25 mg on day 1 (either Monday or Tuesday depending on clinic closures and scheduling), they return the following day and several of the procedures from the previous day will be repeated, including a drug screen for recent opioid use and vitals to include orthostatic measurements. If the drug screen is negative for opioids and no orthostasis is present, then the participant will be administered clonidine, followed 20-40 min later by oral NTX (6.25 mg if Tuesday or 12.5 mg if Wednesday). Participant's orthostatic vital signs and symptoms will be monitored prior to and 20 minutes following clonidine administration as well as 2 hours after oral naltrexone administration. Procedures for release from the clinic will occur as in day 1. Participants will return on two subsequent days to undergo several procedures as before and receive clonidine followed 20-30 min later by increasing doses of oral NTX under observation, and receive the NTX injection on day 5. Participants then attend clinic once per week for up to 8 weeks (weeks 5-12).

If participants do not receive naltrexone on day 1 of week 4 (e.g., Monday was a holiday so did not attend clinic) then the following will occur: Participants will attend clinic on day 2 of week 4 and submit a urine sample that may need to be opioid-negative in order to start NTX induction. (If the urine sample is positive for opioids then the decision to start NTX induction will be made by a study physician; participants have up to day 3 to be inducted onto NTX). Upon confirmation of an opioid-negative urine sample or determination by study physician to proceed with NTX induction, participants will be administered clonidine, followed by oral NTX (6.25 mg). If the sample is negative or regular use is not indicated, participant's orthostatic vital signs and symptoms will be monitored prior to and 20 minutes following clonidine administration as well as 2 hours after initial oral naltrexone administration. If the participant experiences lightheadedness or dizziness and has evidence of orthostatic hypotension with

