Participants who successfully transition to NTX injection in week 4 will be offered the opportunity to receive one additional NTX injection in week 8. In order to be eligible for the second NTX injection, participants submit a urine sample that may need to be opioid-negative to receive NTX injection during week 8. If the urine sample is positive for opioids then the decision to give the second NTX injection will be made by a study physician. If the study physician determines that the participant will not receive the second NTX injection, they will be referred to appropriate alternative treatment, if desired. Otherwise, participants continue in the study as before, attending weekly clinic visits for individual psychotherapy and completion of assessments. All participants will attend their last clinic visit during week 12 to complete final assessments, terminate therapy, and receive aftercare referrals as determined during the course of treatment. A follow-up interview will be conducted during week 16 (+/- 1 week). Participants will receive an appointment reminder at least one day prior to each appointment during the NTX phase to increase attendance. Participants will be asked to supply names and phone numbers of at least two stable contact people whom staff can call if the participant can't be reached post-participation. Staff will maintain at least monthly contact with participants who have been discharged from the trial to enhance follow-up rates. In advance of the scheduled follow-up appointment, a reminder letter will be sent to each participant's most recently recorded address.

Assessments will typically be obtained once or thrice weekly (more often during week 4). A supervised urine sample will be obtained and self- and observer-ratings completed. Blood samples will also be drawn during week 4 to determine buprenorphine and gabapentin levels.

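### No pregnancy test is required before the optional second depot naltrexone injection in week 8, about 26 to 34 days after the last scheduled test

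*Protocol*

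**What the plan says.** Section 6.C.1 sets the schedule: "Women of childbearing potential will have a pregnancy test before starting the study and prior to oral NTX". Any other test depends on the woman: "If a woman suspects she has conceived during the study a pregnancy test will be done at her request". The pregnancy row of Table 1 (Section 7.I) matches this, with one mark under pre-treatment and one under days 1 and/or 2 of the naltrexone transition. Its cells for the weekly Phase II visits and for week 16 are empty.

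The first depot dose falls in week 4 (Section 7.C): "If 25 mg is tolerated, then on the morning of day 5, participants will receive the depot NTX injection". Weekly visits follow in weeks 5 to 12 (Section 7.B). Those who had the first injection may have one more, and under Section 7.C they "will do so during their week 8 clinic visit". Section 7.B gives the condition: "In order to be eligible for the second NTX injection, participants submit a urine sample that may need to be opioid-negative". If that urine is positive, a study physician decides. Section 7.H repeats the rule. Section 7.C adds a quarantine case: "If a participant is unable to provide a urine drug screen at week 8 due to quarantine, they will not be eligible" for the second injection; Section 14.B, item 9, says the same. None of these places mentions pregnancy.

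Elsewhere the protocol treats pregnancy as a reason not to dose. Section 6.B, item 8, excludes women who "are pregnant, plan to become pregnant, have inadequate birth control, if relevant, or lactating". Section 13, item 6, names pregnancy among the precautions for injectable naltrexone. Section 7.H withdraws a participant whose pregnancy test turns positive. Section 14.B, item 3, asks women who could conceive to use effective contraception and to tell the physician if their plans change. The SAP does not deal with the matter.

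**The concern.** The plan does not rely on the entry test alone. It tests again about three weeks later, before the first naltrexone dose. About four weeks after that it offers another depot dose with no test. The withdrawal rule in Section 7.H can act only on a test that is done, and after week 4 a test is done only if the woman suspects conception and asks.

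Staff who follow the protocol exactly could therefore give a second depot injection to a woman whom the same protocol would withdraw had she been tested. What is at stake is an avoidable exposure of an individual participant. The primary outcome, the power statement and the planned models are untouched.

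**Working it through.** The documents give no figure to reproduce here. The check has three parts: what controls the second injection, how long the untested interval is, and how many conceptions might fall within it.

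**1. Conditions for the second injection**

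- Section 7.B: first injection received; week-8 opioid urine; physician decision if positive.
- Section 7.C: found eligible and chooses the injection; not eligible if quarantine prevents the week-8 urine.
- Section 7.H: physician decision if the week-8 urine is not opioid-free.
- Section 14.B, item 9: quarantine rule repeated.
- Section 6.C.1 and Table 1: no scheduled pregnancy test after the week-4 transition.

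Text and table agree, so this is a gap in the schedule and not a conflict between sections.

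**2. Interval since the last scheduled test** (day 1 of week 1 = study day 1)

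- Test on day 1 or 2 of week 4 = study day 22 or 23. Induction may start as late as day 3, so the test could fall on study day 24.
- Week 8 = study days 50 to 56.
- Shortest interval: 50 − 24 = 26 days. Longest: 56 − 22 = 34 days.
- First depot injection: day 5 of week 4 = study day 26, which is 26 − 24 = 2 to 26 − 22 = 4 days after the test.

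All but the first 2 to 4 days of the interval thus come after the first injection.

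**3. Expected conceptions in the interval**

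Input from the documents: 106 participants anticipated to remain for the naltrexone transition (Sample Size, protocol Section 8 and SAP).

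Assumed inputs, none in the documents: 40–50% women; 25–60% of them receiving both injections; annual contraceptive failure f of 1–10%.

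- Women re-injected: 106 × 0.40 × 0.25 = 10.6 to 106 × 0.50 × 0.60 = 31.8.
- Probability of conception in 4 weeks = 1 − (1 − f)^(4/52). For f = 1%: 0.0773%. For f = 10%: 0.807%.
- Expected number, low: 10.6 × 0.000773 = 0.008. High: 31.8 × 0.00807 = 0.26.

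Sensitivity to the interval, with exponent days/365:

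- 26 days, low inputs: 10.6 × [1 − 0.99^(26/365)] = 10.6 × 0.000716 = 0.008.
- 34 days, high inputs: 31.8 × [1 − 0.90^(34/365)] = 31.8 × 0.00977 = 0.31.

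These figures count every conception in the interval. They are not reduced for conceptions the woman suspects, for those too recent to detect, or for women not of childbearing potential (enrolment runs to age 64). In the other direction, a conception too recent to show at the week-4 test is not counted, though a week-8 test could find it.

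**The case against.** The strongest reply is that the protocol already has layered protection and that a third test is a matter of preference. Inadequate contraception is an exclusion, and two tests are scheduled, the second before any naltrexone. A test is available on request, women are asked to report changed contraceptive plans, and symptoms are asked about at every visit. The investigators may also discharge anyone whose health they think is at risk. The expected yield is well under one case, and most of the interval follows a depot dose that a week-8 test cannot undo.

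Much of this stands, and it is why the point is minor. These safeguards lower the risk but do not detect an unsuspected contraceptive failure. Symptom questions are a weak substitute: Section 13, item 6, lists nausea, vomiting and tiredness as common effects of the injection, so such complaints could be put down to the drug.

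The reply is also right about several stronger readings that a reader might infer:

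- That the depot dose cannot be taken back once given. The documents say only that its effects wear off; irreversibility would be the reader's inference, and the gap does not depend on it.
- That the documents establish harm to a pregnancy. Section 13, item 6, lists pregnancy as a precaution; the stated contraindications are hypersensitivity and acute hepatitis or liver failure.
- That 0.26 is an upper bound. It is the top of a range set by assumed inputs, and the longest interval alone moves it to 0.31.

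Finally, Section 7.A sends laboratory tests to outside laboratories, and Section 14.B, item 3, refers to a urine pregnancy test without saying that it is done on site. A same-visit result therefore cannot be taken for granted and has to be written into the fix.

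**Conclusion.** The gap holds, as a cheap safety improvement to consider. No pregnancy test is required between the week-4 transition and the second depot injection, an interval of about 26 to 34 days on the visit schedule. The expected number is well below one in the trial: roughly 0.01 to 0.26 conceptions of any kind over about 4 weeks. That range rests on the documented 106 and on assumed shares of women, of re-injection and of contraceptive failure; different assumptions would move it. A week-8 test would spare a woman only the second exposure, and it could miss a very recent conception.

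A reader might also infer that the protocol contradicts itself, or that trial results are at risk. Neither is supported: Section 6.C.1 and Table 1 agree with each other, and no analysis depends on this point. The case for change is that the protocol already means to avoid this exposure and the specimen needed is already in hand.

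**What to change.** For women of childbearing potential, require a negative urine pregnancy test, run on site on the urine already collected at the week-8 visit, before the second naltrexone injection.

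- Sections 7.B and 7.C: add this as a condition for the second injection.
- Section 6.C.1: add *and prior to the second NTX injection* to the sentence on scheduled tests.
- Table 1: mark the pregnancy row in the weekly Phase II column with a new footnote, *week 8 only, before second injection*. The existing double-asterisk footnote covers weeks 8 and 12 and would not fit.
- Section 7.A: state that this test is done on site, as an exception to the use of outside laboratories.
- Section 7.H needs no change, since it already withdraws a participant who tests positive.

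Cost: about 11 to 32 urine kits (10.6 to 31.8 women on the assumptions above) and a short wait for each result. With on-site testing there is no extra visit or specimen. Week-8 urine is already part of the eligibility decision, and a participant who cannot give it because of quarantine is already ineligible.
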